### 7.3 Prior and Concomitant Medication

Prior and concomitant medication will be summarised using the WHO dictionary by ATC classification 1st level (alphabetically), ATC classification 2nd level (in decreasing order of frequency) and treatment group for the safety analysis set. These medications will be tabulated separately for:

- 1) Prior medication; i.e. medication taken exclusively prior to treatment (i.e. with stop date before date of first IMP administration);
- 2) Concomitant medication, i.e. medication taken during the treatment period (i.e. medication that was not stopped before date of first IMP-administration [and not started after the last visit date (i.e., visit 6)]).

If the timing of the dose of a medication cannot be established in relation to the administration of IMP, it will be considered as concomitant medication.

### 7.4 Physical Examination

Subjects with abnormalities at any screening, baseline, or post-baseline visit will be listed with all physical examination evaluations for the safety population.

## **8 Exposure and Treatment Compliance**

### **8.1.1 Extent of Exposure**

The number of patients that completed IMP treatment, the number of patients that took each dose of IMP and the number of patients that did not take any amount of IMP will be summarized and listed by treatment group for the safety analysis set.

### **8.1.2 Treatment Compliance**

The number and proportion of subjects deviating from the treatment regimen will be summarized by treatment group for the safety population. The summary will include the following:

- the number of patient that did not consume the entire dose,
- deviations from protocol mandated administration time,
- the number of patients that did not fast two hours before colonoscopy,
- the number of patient that did not adhere to clear liquid diet 24 hours prior to colonoscopy and
- the number of subject that did not consume the recommended number eight-ounce glasses of clear liquid after each dose of IMP.

Furthermore, associated listing will be produced.

## 9 Efficacy

### 9.1 General Considerations

All statistical tests will be performed using a two-sided test at a 5% significance level.

The primary and secondary efficacy analyses will be conducted for the mITT analysis set. Continuous variables will be described with the number of non-missing values, mean, standard deviation, median, and minimum/maximum values. Categorical variables will be described with the number and percentage of subjects within each level.

In order to preserve the type I error for testing for the primary endpoint of the overall colon cleansing and the secondary endpoint of right colon cleansing, the NI for evaluating the cleansing within the right colon will only be assessed if NI is demonstrated for the primary endpoint using the mITT population. Superiority for the primary endpoint will be assessed if and only if NI is demonstrated for both the primary efficacy endpoint and the secondary right colon efficacy endpoint.

### 9.2 Primary Endpoint(s)

The primary endpoint is the Proportion of subjects classified as a responder defined by “excellent” or “good” using the Modified Aronchick scale.

#### 9.2.1 Primary Variable(s) Analysis

For primary analysis what is of interest is the assessment of the difference in responder rates in overall colon cleansing between NaP/MC Oral Solution and PREPOPIK®. A subject is considered to be a “responder” if overall colon cleansing is classified as either “excellent” or “good” by the blinded endoscopist using the Modified Aronchick Scale (see [Appendix 3](#) ). The NI margin for the difference between treatments (NaP/MC Oral Solution minus PREPOPIK®) will be -8% (absolute). The NI hypothesis to be tested for the primary endpoint will be:

$$H_0: \pi_{\text{NaP/MC Oral Solution}} - \pi_{\text{PREPOPIK}^{\circledR}} \leq -8\%$$

against the alternative

$$H_1: \pi_{\text{NaP/MC Oral Solution}} - \pi_{\text{PREPOPIK}^{\circledR}} > -8\%,$$

where  $\pi_{\text{NaP/MC Oral Solution}}$  and  $\pi_{\text{PREPOPIK}^{\circledR}}$  denote the true percentage of subjects classified as responders (i.e., excellent and good according to the Modified Aronchick Scale (see [Appendix 3](#) )) among subjects treated with NaP/MC Oral Solution or PREPOPIK®, respectively, for colon cleansing in preparation for colonoscopy.

The null hypothesis ( $H_0$ ) will be tested against the alternative by constructing a 2-sided 95% confidence interval for the difference in responder rates. The primary analysis will be stratified by the stratification factor, site, by using the Mantel-Haenszel method to combine results across sites. In brief, this corresponds to deriving a weighted average across sites where the weight depends on the number of observations in each treatment group in each stratum (see [Appendix 2](#) for more details). Subjects who do not have an excellent or good rating according to the Modified Aronchick Scale (see [Appendix 3](#)) for any reason will be considered treatment failures (i.e., not a responder). Hence, treated patients that did not complete the colonoscopy assessment will be classified as non-responders. If the lower limit of the 95% confidence interval is greater than the margin (-8%), the null hypothesis will be rejected and it will be claimed that NaP/MC Oral Solution is non-inferior to PREPOPIK® with respect to colon cleansing in preparation for colonoscopy.

If NI is demonstrated for both the primary efficacy endpoint and the secondary efficacy endpoint for the right colon (see [Section 9.3.1](#)), and if the lower bound for the primary analysis results in a confidence interval that is above 0% then, superiority will be declared for the primary endpoint. Hence, this superiority test will be conducted at one sided significance level of 2.5%.

## 9.2.2 Sensitivity Analyses

As a sensitivity analysis, the NI analysis in [section 9.2.1](#) will be repeated using the per-protocol population.

For the primary analysis, if a patient does not have efficacy assessment (colonoscopy), it is considered to be a treatment failure. There are two main reasons for applying such method of imputations. First, the number of patients missing efficacy assessment is expected to be very low. In the two pivotal Ferring studies (FE2009-01 and FE2009-02), the number of patients that were treated but did not have colonoscopy assessment were less than 1%. Furthermore, if the reason for not having efficacy assessment is related to tolerability then these can also be considered as treatment failures and treating such missing values as failures is appropriate. However, in this study, if the number of treated patients that do not have efficacy assessment for reasons other than tolerability is  $\geq 0.5\%$ , there will be a sensitivity analysis, where, a multiple imputation method will be applied to impute for such missing colonoscopy assessment. Details of the multiple imputation method to be applied is found in [Appendix 2](#)

The patients that do not have colonoscopy results for other than tolerability issues will be identified using the question “was colonoscopy performed at this visit?” on the colonoscopy & assessment eCRF page. Using the “specify” responses to this question, prior to data base lock, the clinical team will review and categorize the reasons for not performing or completing colonoscopy. One of the classification categories will be “tolerability”. If there are  $\geq 0.5\%$  patients that did not have colonoscopy performed or completed for reasons other than “tolerability” a sensitivity analysis will be performed by applying multiple imputation method to impute for such missing assessments.

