6.3 Procedure/Colonoscopy Visit (Visit 3)

If the subject is participating in the PK subset, additional laboratory samples will be obtained for sodium picosulfate and BHPM at the following timepoints:

- 15 minutes before the second dose of IMP
- 1 to 2 hours after the second dose of IMP
- 3 to 6 hours after the second dose of IMP

Immediately prior to the colonoscopy, a PK sample will be obtained for **all participating subjects** in the study (approximately 2 hours prior to the colonoscopy).

Before the colonoscopy, the following will be performed:

- Treatment completed
- Collect Subject Diary Card
- Collect the Acceptability and tolerability completed questionnaire*
- Obtain orthostatic vital signs (blood pressure and pulse)
- Measure body weight
- Obtain laboratory sample (chemistry, hematology)
- Adverse events (recorded by study personnel)
- Document any concomitant medications

- PK subset only: PK samples for sodium picosulfate and BHPM 15 minutes before the second dose, and 1 to 2 hours and 3 to 6 hours after the second dose of the IMP
- All subjects: PK sample immediately prior to colonoscopy (approximately 2 hours prior to the colonoscopy)
- Perform study drug accountability by the unblinded coordinator or unblinded pharmacist (if applicable)

*Subjects should be instructed to fill out the questionnaire during the visit in a private area prior to contact with the Investigator and to return the completed questionnaire to the study coordinator. If the coordinator is not available during the procedure, the subject will put the completed questionnaire in a sealed envelope and provide it to a member of the surgical team. The study coordinator should check each questionnaire for completion, and if the subject did not answer all/some of the questions, note the reasons on the first page of the questionnaire. No one (including study coordinator or a family member) should interpret questions or response choices for the subject.

During the colonoscopy procedure, the blinded endoscopist will:

- Video-record the colonoscopy
- Use the Modified Aronchick Scale (see [Appendix C](#)) to score the quality of the bowel preparation in the overall colon after use of the study drug
- Use the Boston Bowel Preparation Scale (see [Appendix C](#)) to score the quality of the preparation in the different segments of the colon after use of the study drug
- Record the outcome of the colonoscopy

After the colonoscopy procedure, the following will be performed/recorded:

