7.1 Assessments Related to Endpoints

7.1.1 The Modified Aronchick Scale

The efficacy of overall colon cleansing will be measured by a blinded endoscopist using the Modified Aronchick scale. The overall colon will be graded as “Excellent”, “Good”, “Fair”, or “Inadequate” according to the definitions in [Table 2](#).

Table 2 Modified Aronchick Scale

Grade	Description
Excellent	>90% of mucosa seen, mostly liquid stool, minimal suctioning needed for adequate visualization
Good	>90% of mucosa seen, mostly liquid stool, significant suctioning needed for adequate visualization
Fair	>90% of mucosa seen, mixture of liquid and semisolid stool, could be suctioned and/or washed
Inadequate	<90% of mucosa seen, mixture of semisolid and solid stool which could not be suctioned or washed

The subject is considered to be a responder if overall colon cleansing equals “excellent” or “good” on this four-point scale.

The blinded endoscopist will record in the eCRF whether or not the colonoscopy was completed. If the colonoscopy was not completed, he/she will need to state the reason why and whether a repeat is required.

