7.1.2 The Boston Bowel Preparation Scale

The efficacy of right colon cleansing, transverse colon cleansing, and left colon cleansing will be measured by a blinded endoscopist using the Boston Bowel Preparation Scale after washing/suctioning. Colon cleansing will be graded 0, 1, 2, or 3, according to the definitions in The Boston Bowel Preparation Scale (see [Appendix C](#)).²

[figure not shown]

Figure 2 The Boston Bowel Preparation Scale

- 0 Unprepared colon segment with mucosa not seen due to solid stool that cannot be cleared.
- 1 Portion of mucosa of the colon segment seen, but other areas of the colon segment not well seen due to staining, residual stool, and/or opaque liquid.
- 2 Minor amount of residual staining, small fragments of stool and/or opaque liquid, but mucosa of colon segment seen well.
- 3 Entire mucosa of colon segment seen well with no residual staining, small fragments of stool or opaque liquid.

Each region of the colon receives a “segment score” from 0 to 3, and these segment scores are summed for a total BBPS score ranging from 0 to 9. The maximum BBPS score for a perfectly clean colon without any residual liquid is 9, and the minimum BBPS score for an unprepared colon is 0. If an endoscopist aborts a procedure due to an inadequate preparation, then any non-visualized proximal segments are assigned a score of 0.

Both the Modified Aronchick scale and BBPS Scale are attached as [Appendix C](#).

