### SAS code for generating multiple imputed data using *proc mi* procedure ([13])

If the primary endpoint (overall colon cleansing based on Modified Aronchick Scale) is missing for a mITT patient and the assessment is not available due to other than tolerability of the IMP the following SAS code can be used to generate 20 imputed data sets.

```
proc mi seed=xxx out=xxxx n impute=20;
class outcome trt site;
monotone logistic(outcome = trt site);
var trt site outcome;
run;
```

Where  $trt$  represents treatment group and  $site$  represents the patient site.

Once the 20 imputed data sets are generated, for each imputed data the above formula can be used to derive the stratified difference and associated variance i.e.,

Estimated difference:  $\hat{Q} = \sum_{j=1}^s w_j d_j$

Associated Variance:  $\hat{U} = \sum_{j=1}^s w_j^2 \left( \frac{p_{1j}(1-p_{1j})}{n_{1j}} + \frac{p_{2j}(1-p_{2j})}{n_{2j}} \right)$

Let  $\widehat{Q}_j$  and  $\widehat{U}_j$  be the point estimate and associated variance for the  $j$ th imputed data set ( $j=1, \dots, k$ ). Then the point estimate pooling over the imputed data sets would be as follows:

$$\bar{Q} = \frac{1}{k} \sum_{j=1}^k \widehat{Q}_j$$

The within-imputation variance is given by

$$\bar{U} = \frac{1}{k} \sum_{j=1}^k \widehat{U}_j$$

And the between-imputation variance is given by

$$B = \frac{1}{k-1} \sum_{j=1}^k (\widehat{Q}_j - \bar{Q})$$

Finally, the total variance associated with  $\bar{Q}$  is as follows:

$$T = \bar{U} + \left(1 + \frac{1}{k}\right)B$$

Then

$$(Q - \bar{Q})T^{-1/2} \sim T\text{-distribution with } v \text{ degrees of freedom}$$

$$v = (k-1)[1 + \bar{U}/((1+k^{-1})B)]^2$$

[figure not shown]
Where  $Q$  is the population parameter.

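### The conditional multiple imputation exempts only tolerability, so a subject left ungraded because of inadequate cleansing would be imputed as a probable responder

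*SAP*

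**What the plan says.** **Primary analysis.** SAP 9.2.1 counts any subject without an excellent or good grade as a failure, whatever the reason, and adds that "treated patients that did not complete the colonoscopy assessment will be classified as non-responders".

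**Sensitivity analysis.** SAP 9.2.2 defends that rule for tolerability: when a grade is missing because the subject could not tolerate the product, "treating such missing values as failures is appropriate". It then relaxes the rule for everyone else. If at least 0.5% are "patients that did not have colonoscopy performed or completed for reasons other than" tolerability, their missing assessments are multiply imputed. The clinical team sorts the reasons into categories before database lock; tolerability is the only category named and the only one exempt. Appendix 2 applies imputation when the Aronchick grade "is missing for a mITT patient and the assessment is not available due to other than tolerability of the IMP". Its model statement is "monotone logistic(outcome = trt site"), so only treatment and site inform the imputed value. Protocol 9.6.2 also exempts drug tolerability alone.

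**Abandoned procedures.** Protocol 6.3 has both scales scored while the examination is under way ("During the colonoscopy procedure, the blinded endoscopist will" do so). Protocol 7.1.1 adds: "If the colonoscopy was not completed, he/she will need to state the reason why and whether a repeat is required". For the Boston scale, Protocol 7.1.2 says: "If an endoscopist aborts a procedure due to an inadequate preparation, then any non-visualized proximal segments are assigned a score of 0". No corresponding instruction is given for the Aronchick grade.

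**The concern.** This analysis exists to test the missing-equals-failure rule. It does that well when it relaxes the rule only for subjects whose missing grade says nothing about how the preparation worked, such as a scheduling problem. A colonoscopy called off because the bowel was not clean is the opposite case: the reason for the missing grade is the outcome being measured.

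The model cannot know this, because the reason is not in it. Adding a poor-preparation category at the pre-lock review would not help either, since every category except tolerability is imputed. Known efficacy failures would become probable successes, to the benefit of whichever arm had more of them. What is at stake is the accuracy of a supporting robustness result, not the trial's conclusion.

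**Working it through.** **Inputs from the documents.** Responder rate 84% in both arms, margin 8 points, one-sided 0.025, at least 90% power, 450 per arm (SAP 3.2). Imputation trigger 0.5% (SAP 9.2.2). Missing assessments under 1% in the two earlier studies (SAP 9.2.2).

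**Assumptions.** All 450 per arm are treated, and graded subjects respond at 84% in both arms. The documents give no count of subjects left ungraded for poor cleansing, so every count below is assumed.

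**1. The plan's own figure.** n = (1.960 + 1.282)² × 2 × 0.84 × 0.16 / 0.08² = 442 per arm after rounding up, against 450 planned. Power at 450 is 90.5%. The stated sample size is reproduced.

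**2. Trigger.** 0.005 × 900 = 4.5, so 5 subjects missing for non-tolerability reasons start the imputation. Under 1% of 900 means at most 8.

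**3. What imputation does to such a subject.** The Appendix 2 model was simulated with 20 imputations, 12 assumed sites of 75 subjects (the protocol gives 10 to 15 sites) and 60 replicates. Nine test-arm subjects who had truly failed were left ungraded. They were imputed as responders 83% of the time, matching the 83% rate among graded test-arm subjects. The mean difference moved from -1.5 points (kept as failures) to +0.2 (imputed). The size agrees with simple arithmetic: 9 × 0.83 / 450 = 1.66 points.

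**4. Shift per net case.** 0.84 / 450 = 0.187 points. At responder rates of 80% and 90% it is 0.80 / 450 = 0.178 and 0.90 / 450 = 0.200. An even split between arms gives no shift.

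**5. Effect on the lower 95% limit.** If the cases are imputed, the difference is about 0. SE = √(2 × 0.84 × 0.16 / 450) = 2.444 points, and the lower limit is 0 - 1.96 × 2.444 = -4.79%. If n cases in an arm are kept as failures, that arm's rate is 0.84 × (450 - n) / 450:

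| Ungraded for poor cleansing, test v control | Difference, kept as failures | Lower limit, kept as failures | Lower limit, imputed |
|---|---|---|---|
| 1 v 0 | -0.19 | -4.99% | -4.79% |
| 2 v 0 | -0.37 | -5.19% | -4.79% |
| 0 v 2 | +0.37 | -4.44% | -4.79% |
| 5 v 0 | -0.93 | -5.78% | -4.79% |
| 8 v 0 | -1.49 | -6.37% | -4.79% |

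These limits are unstratified and leave out between-imputation variance, which Appendix 2 would add. The last two rows are illustrations that put every missing case in one arm and attribute it to poor cleansing.

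**The case against.** The strongest objection is that the group may not exist. The Aronchick scale has a grade for this event, Inadequate, and the endoscopist scores during the procedure, so an examination abandoned for stool can be graded. What remains is mainly cancellation before insertion, a pathway neither document describes. The eCRF page that would show how such cases are recorded is not among the documents. This stands, and it is why the point is minor. It does not remove the point: SAP 9.2.2 expressly covers procedures not completed, Protocol 7.1.1 asks for the reason, and nothing requires an Aronchick grade when a procedure is stopped or called off.

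Several stronger readings are tempting, and the documents do not support them:

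- *Every procedure abandoned for stool is imputed.* No. Appendix 2 requires the grade to be missing; a subject graded Inadequate stays a failure.
- *The SAP contradicts Protocol 7.1.2.* No. That rule governs Boston segment scores, while the imputation concerns the Aronchick grade. It is an analogy that shows how the protocol treats an abort for poor preparation elsewhere.
- *The SAP breaks its own stated principle.* No. SAP 9.2.2 speaks of tolerability only. Its reasoning extends naturally to failed cleansing, but that extension is an inference.
- *The SAP departs from the protocol here.* No. Protocol 9.6.2 draws the same line, so the gap is in both documents.
- *1.49 points is the most it could be.* No. The under-1% figure describes two earlier studies and does not bound missingness in this trial.

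**Conclusion.** The point holds as a minor one. As written, the conditional imputation treats a subject left ungraded for inadequate cleansing as if the grade were missing for a reason unrelated to the preparation, and imputes a responder about 84% of the time under the design assumption. Each net case in one arm moves the sensitivity difference by about 0.19 points, and the error favours the arm with more such cases.

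A reader might infer that the non-inferiority claim is at risk. It is not: that claim and any superiority claim rest on the primary analysis and the right-colon result, and the primary analysis already counts these subjects as failures. Every illustrative lower limit above also clears -8%, but that depends on the assumed equal 84% rates. Confidence in the reading of the text is high; how many subjects it would touch cannot be known from the documents.

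**What to change.** In SAP 9.2.2 and Appendix 2, keep subjects ungraded because of tolerability or inadequate bowel preparation as non-responders, and impute only grades missing for reasons unrelated to the preparation. Count the 0.5% trigger on the same set. Assign the reasons in the pre-lock review already planned, from the non-completion reason already collected. Because Protocol 9.6.2 names tolerability alone, record the change in SAP section 12.

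The cost is one more exempt category, one line in each of the two SAP places, and the section 12 entry. The sample size and primary analysis do not change. Responder rates in the sensitivity analysis may be slightly lower, and if all missing cases prove to be poor cleansing it will reproduce the primary result.

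Requiring an Aronchick grade of Inadequate whenever a procedure is abandoned for stool would settle most cases at source, but it has to be in force when the procedures are done. The SAP change needs only to precede database lock.

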### **9.3 Secondary Endpoint(s)**

#### **9.3.1 Assessing the Cleansing of the Right Colon**

The Boston Bowel Preparation Score (BBPS) will be used to assess the cleaning of the right colon. The difference between the responder rates in the right colon cleansing using NaP/MC Oral Solution or PREPOPIK® will be assessed. A subject is considered to be a “responder” if the BBPS (Right Colon) score is  $\geq 2$ . Using the mITT population and the analysis methodology described for the primary endpoint a 95% two-sided confidence interval for the responder rate difference of NaP/MC Oral Solution minus PREPOPIK® will be constructed. If the NI objective is met for the primary endpoint, these CIs will be used to assess the NI of NaP/MC Oral Solution to PREPOPIK® in the cleansing of right colon as assessed by BBPS. The NI margin for the testing the difference between treatments (NaP/MC Oral Solution minus PREPOPIK®) for cleansing of the right colon is again set to be -8% (absolute). Hence, if the lower bound of this confidence interval exceeds -8.0% then NaP/MC Oral Solution will be declared non-inferior to PREPOPIK® with respect to the cleansing of the right colon.

